**Events NOT meeting UPIRSO criteria:**

Events that do NOT meet UPIRSO criteria should be tracked, evaluated, summarized, and submitted to the UTSW HRPP/IRB at continuing review.

For more information on UTSW HRPP/IRB reportable event policy, see <https://www.utsouthwestern.edu/research/research-administration/irb/assets/policies-combined.pdf>.

**7.3 Unblinding Procedures**

N/A. There is no blinding in this study.

**8.0 STATISTICAL CONSIDERATIONS**

### **8.1 Study Design/Study Endpoints**

The primary endpoint of this study is diagnostic performance (sensitivity and specificity) measured as area under the curve (AUC) in the response assessment. Key secondary and exploratory endpoints include correlation between pre-operative CEDM lesion size and final pathology and assessment of timing of CEDM for best performance in predicting pathologic response.

### **8.2 Sample Size and Accrual**

Due to the exploratory nature of the study and lack of reliable prior information, a formal sample size calculation was not done. We are proposing to accrue 100 patients for enhanced certainty of our descriptive statistics. We assume 40% prevalence of pCR. A sample of 100 patients will provide 95% confidence intervals of at most (maximum)  $\pm$  0.17 (for sensitivities),  $\pm$  0.14 (for specificities) and  $\pm$  0.12 (for AUC). Simple asymptotic with continuity correction and normal approximation was used for calculation for sensitivity and specificity. Binormal approximation was used for the calculation for AUC. Assuming one lesion per patient, 100 patients will provide 95% confidence interval of spearman rank correlation of lesion size with a width no larger than 0.39. Fisher's transformation followed by a normal approximation was used for calculation. Results from this study would help us design a multi-institutional study allowing comparison to other imaging modalities with a larger patient cohort.

### **8.3 Data Analyses**

Descriptive statistics will be produced for all patients; frequencies and percentages for categorical measures and means, medians, standard deviations, and ranges for continuous measures. The number of cancer foci identified by each imaging modality will be compared. Tumors will be categorized according to immunohistochemical approximated molecular profiles (Luminal A, Luminal B, Triple-negative and HER-2 amplified). Additional exploratory analyses will be performed as needed.

#### **1. Sensitivity of CEDM versus mammography**

Histopathological assessment will be used as the reference standard.

For categorical measurements of tumor response (CR/PR/SD/PD or RCB0-I /RCB II /RCB III):

1. Sensitivities and specificities in predicting pCR (or RCB0) will be calculated for CEDM and mammography respectively.
2. The agreement between CEDM and mammography in categorizing tumor response (CR/PR/SD/PD or RCB0-I/ RCBII/RCBIII) will be assessed using weighed kappa.

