## 2.4 Endpoints

2.4.1 Primary: Diagnostic performance (sensitivity and specificity) measured as area under the curve (AUC) in the response assessment by varying metrics including pCR and RCB classification.

2.4.2 Secondary: Correlative statistic for CEDM lesion sizing vs pathologic lesions sizing, frequency of finding additional sites of disease in ipsilateral or contralateral breasts by CEDM and number of such new lesions.

2.4.3 Exploratory: AUC of CEDM using varying time points for CEDM, survey scores for patient experience with CEDM

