**6.1 Response Evaluation Criteria**

Response evaluation criteria in solid tumors (RECIST) 1.1 criteria, considering the sum of the largest dimension of malignancies at baseline and its variation at subsequent measurements . Clinical response is classified as follows: complete response (CR, disappearance of all lesions); partial response (PR,  $\geq 30\%$  dimensional reduction), stable disease (SD,  $< 30\%$  dimensional reduction/ $< 20\%$

Study Number – Insert PRMC Assigned SCCC- Protocol Number (found on the PRMC approval letter)

---

dimensional increase) and progressive disease (PD,  $\geq 20\%$  dimensional increase).

**For pathologic response, RCB index is assessed routinely per standard of care, where a complete pathologic response has an RCB of zero, and residual disease is classified into three categories (RCB-I, RCB-II, and RCB-III)**

[http://www3.mdanderson.org/app/medcalc/index.cfm?pagename=jsconvert\\_3](http://www3.mdanderson.org/app/medcalc/index.cfm?pagename=jsconvert_3)

---

**6.1.2** This is not a treatment study. Patients will be treated either as per standard of care neoadjuvant protocol or as part of ongoing treatment trials in the UT Southwestern Medical Center.

Percent change in tumor volume using the following formula for ellipsoidal/spherical volume derived from mid-dynamic sequence subtraction series:  $V (\text{cm}^3) = (4/3 \pi) \times \text{length}/2 \times \text{width}/2 \times \text{height}/2$

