#### **2. For continuous measurements of tumor response (RECIST, percent change in tumor volume and pre-surgery lesion size):**

1. ROC analysis will be used to assess the diagnostic performance of CEDM and mammography. The Area under the ROC curve (AUC) will be compared. A leave-one-out cross validation algorithm will be used to reduce bias from overfitting.
2. The agreement between CEDM and mammography in RECIST, percent change in volume and pre-surgery lesion size will be assessed using intraclass correlation (ICC).

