#### **Post Neoadjuvant Therapy ypT Classification**

Preoperative or neoadjuvant systemic therapy has been used for several decades for managing inflammatory and locally advanced breast cancer, and it is being used increasingly for managing earlier stages of the disease, as well. Clinical (pretreatment) T (cT) is defined by clinical and radiographic findings; pathological (posttreatment) T (ypT) is determined by the pathological size and extent of disease – this can only be determined if the primary site is resected after completing neoadjuvant therapy. The ypT is determined by measuring the largest contiguous focus of residual invasive tumor, with the modifier "m" indicating multiple foci of residual tumor. The measurement of the largest tumor focus should not include areas of fibrosis within the tumor bed. The inclusion of additional information in the pathology report may further assist the clinician in estimating the extent of residual disease. The residual cancer burden method (www.mdanderson.org/breastcancer\_RCB) can be recommended, with demonstrated prognostic relevance within each molecular subtype of breast cancer, and provision of quantitative information that is complimentary to yp classification. Other methods, currently without subtype-specific prognostic evidence, semi-quantitatively compare the histopathology before and after treatment, e.g. Miller-Payne, Chevallier, Sataloff, or others. Otherwise, description of the distance over which tumor foci extend, the number of tumor foci present, or the number of slides/blocks in which tumor appears, might be offered in the report.

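### RCB is named in the primary endpoint and its numeric index is assessed routinely, but no planned analysis uses that index, and beyond RCB-0 (pCR) the classes used merge RCB-0 with RCB-I

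*Combined protocol and SAP*

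**What the plan says.** - **Endpoint (2.4.1).** Diagnostic performance is "measured as area under the curve (AUC) in the response assessment by varying metrics including pCR and RCB classification". The hypothesis in section 1.3 also names both pCR and RCB.
- **Reference standard (6.1).** "For pathologic response, RCB index is assessed routinely per standard of care, where a complete pathologic response has an RCB of zero". Residual disease is then divided into RCB-I, II and III, so the plan recognises four levels. The staging extract in Appendix C credits the RCB method with "provision of quantitative information that is complimentary to yp classification".
- **Categorical analyses (8.3, item 1).** Under the line "For categorical measurements of tumor response (CR/PR/SD/PD or RCB0-I /RCB II /RCB III") there are two analyses. The first is sensitivity and specificity of each modality for pCR, with RCB0 given as an equivalent. The second is a weighted kappa between CEDM and mammography on CR/PR/SD/PD or on RCB0-I/II/III. Section 6.3 repeats the RCB kappa.
- **Continuous analyses (8.3, item 2).** "ROC analysis will be used to assess the diagnostic performance of CEDM and mammography", and the AUCs are to be compared. The measures listed are RECIST, percent volume change and pre-surgery lesion size. The binary reference for these curves is not stated.
- **Correlation (8.3, item 3).** Spearman correlation is planned for imaging size against pathologic tumour size, not against RCB.
- **Size (8.2).** "We are proposing to accrue 100 patients for enhanced certainty of our descriptive statistics"; "We assume 40% prevalence of pCR". No alpha, effect size or power is given, and the section says that no formal sample size calculation was done.

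**The concern.** RCB is presumably in the endpoint because it grades residual disease, which pCR cannot do. The planned analyses do not use that grading against imaging. RCB0 versus the rest is pCR under another name. The only other use groups RCB-0 with RCB-I, which removes the distinction the primary objective is about, and that use is an agreement statistic between the two modalities with no pathology reference.

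An ordinary AUC needs a two-way reference, so reporting an AUC by RCB class means choosing a cut, such as 0-I against II-III. None is written down, and a cut chosen after the data are seen is open to selection. A second binary cut also has about the same precision as the pCR AUC and so adds little.

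The imaging measures are continuous and the RCB index is numeric. Whether CEDM follows residual burden more closely than mammography could be estimated on the full scale from data that routine care already produces. Section 8.2 says the results are meant to help design a multi-institutional study, so the precision of these estimates matters.

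**Working it through.** **1. The plan's own figures, which hold** (n=100, 40 pCR and 60 non-pCR).
- Sensitivity: 1.96·√(0.25/40) + 1/80 = 0.167, stated ±0.17.
- Specificity: 1.96·√(0.25/60) + 1/120 = 0.135, stated as at most ±0.14.
- AUC at 0.5: 0.113 (binormal) or 0.116 (Hanley-McNeil), stated ±0.12.
- Spearman at zero correlation: 2·tanh(1.96/√97) = 0.393, stated 0.39.

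The sizing arithmetic is not in question.

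**2. Where RCB appears in the analyses.**

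| Analysis | Form of RCB |
|---|---|
| Sensitivity, specificity (8.3 item 1) | RCB0 vs rest, i.e. pCR |
| Weighted kappa (6.3; 8.3 item 1) | 0-I / II / III |
| ROC and ICC (8.3 item 2) | RCB index not listed |
| Spearman (8.3 item 3) | none; pathologic size |

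The numeric index appears in none of them.

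**3. How many patient pairs each coding can rank.** Take n=100 and 40% pCR from section 8.2. Assume RCB-0/I/II/III shares of 40/15/30/15 (the I/II/III split is not in the documents) and no ties among non-zero indices.
- Numeric index: 100·99/2 − 40·39/2 = 4950 − 780 = 4170
- Four classes: 40·60 + 15·45 + 30·15 = 3525
- Three merged classes: 55·45 + 30·15 = 2925
- 0-I vs II-III: 55·45 = 2475
- pCR vs rest: 40·60 = 2400

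Pairs are not equally informative, so this shows direction only.

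**4. Illustrative power, Spearman version.** Simulated trivariate normal with 40% of patients at RCB 0 and n=100. Assumed correlations: CEDM with burden 0.7, mammography with burden 0.5, the two modalities with each other 0.5. The difference between dependent correlations is tested by the Meng-Rosenthal-Rubin method, two-sided 5%, with 4,000 to 6,000 replicates.

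| Shares 0/I/II/III (%) | Index | Four classes | Three merged | pCR only |
|---|---|---|---|---|
| 40/10/40/10 | 66.4 | 61.3 | 56.7 | 49.4 |
| 40/15/30/15 | 69 | 66 | 58 | 50 |
| 40/20/35/5 | 66.9 | 62.8 | 52.4 | 49.8 |
| 40/25/25/10 | 67.1 | 65.0 | 50.1 | 50.4 |
| 40/30/20/10 | 65.7 | 63.4 | 44.1 | 48.4 |

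The index gains 9.7 points over three merged classes in the first row and 21.6 in the last. Unmerging alone recovers 61.3 − 56.7 = 4.6 of the 9.7 points when RCB-I is 10%, and 63.4 − 44.1 = 19.3 of the 21.6 when it is 30%. Over all settings tried, the gain over three merged classes ran from 0 (no true difference) to about 25. It was most often 6 to 16, and values above 20 mostly needed an RCB-I share near 30%.

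**5. Illustrative power, concordance version.** Same n and pCR rate, jackknife standard errors, 1,500 replicates, RCB-I/II/III at 12/33/15%. With latent correlations of 0.7 and 0.5 and error correlation 0.3, power was 45% (0-I vs II-III), 55% (three merged classes) and 62% (index). Across repeated runs with varied correlations and class shares, the index gained about 4 to 17 points over three merged classes, about 9 to 25 over the binary cut, and about 1 to 8 over four classes. With no true difference, rejection was 4 to 5%.

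**6. Precision, the plan's own yardstick.** In one set of concordance runs the 95% half-width for CEDM was 0.072-0.101 for the 0-I vs II-III AUC, 0.073-0.101 for the pCR AUC and 0.054-0.069 for concordance with the index. The last is a different estimand, so the comparison is indicative. The first two are nearly identical.

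**The case against.** Two stronger readings are tempting, and the documents support neither.

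A reader might infer that RCB is analysed only as three merged classes. It is not: item 1 of section 8.3 separates RCB0 from the rest, so the accuracy analysis does see the pCR distinction.

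A reader might also infer that the plan forfeits 10 to 25 points of power for CEDM against mammography. That figure compares the index with a 0-I versus II-III AUC that the plan never specifies. The merged classes are assigned only to a between-modality kappa, which is not a test of either modality against pathology. The natural reference for the AUC comparison in item 2 is pCR, and the proposal leaves that alone. The plan states no power or alpha, calls itself exploratory and is sized on interval width.

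Further objections carry some weight. Every simulation input except n and the pCR rate is assumed, and a single latent burden behind both imaging and RCB favours a full-scale index. Four unmerged classes come close to the index unless RCB-I is uncommon. Section 8.3 allows additional exploratory analyses as needed, so a numeric RCB analysis is not precluded. Concordance is a different estimand from the AUC named in 2.4.1, and adopting it needs an amendment under section 9.6.

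What remains is that a named component of the primary endpoint has no stated route to an AUC, and its routinely available numeric form is left out of every planned analysis. A general allowance for exploratory work does not replace pre-specification for a metric in the primary endpoint.

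**Conclusion.** The point holds as a specification gap with a cheap, more precise remedy. It is not a demonstrated loss of planned power. From the text alone: no planned analysis uses the numeric RCB index; beyond pCR, RCB enters only a kappa in which pCR and non-pCR patients share a class; and the AUC by RCB classification needs a cut that is not given.

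The size is illustrative. At n=100 and 40% pCR, using the index adds about 4-17 points of power for the paired difference over three merged ordered classes and about 10-25 over a second binary cut. The Spearman version goes outside the first range at the extremes: zero with no true difference, up to about 25 when RCB-I is near 30%. Unmerging to four classes recovers much of the gain when RCB-I is not rare. These figures rest on assumed correlations, RCB-I/II/III shares and a two-sided 5% test, none of which is in the documents. The change is worth making, but the pCR analyses do not depend on it.

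**What to change.** 1. Keep the pCR (RCB-0) sensitivity, specificity and AUC unchanged as the primary accuracy analysis.
2. Record the numeric RCB index in REDCap.
3. For the RCB metric in 2.4.1 and 8.3, pre-specify the concordance index of each modality's continuous measure with the RCB index: among pairs of patients with different indices, the probability that the one with the higher index has the worse imaging measure, leaving out pairs tied at RCB 0. Spearman correlation is an acceptable alternative. Report CEDM, mammography and their paired difference with a bootstrap or jackknife 95% CI.
4. Use four classes (RCB-0, I, II, III) wherever classes are shown or enter a kappa, including section 6.3.
5. Label concordance as a different quantity from the binary AUC and say that the ±0.12 in section 8.2 does not apply to it.

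Cost: a few lines of text in an IRB-approved amendment, one CRF field for a value already assessed in routine care, and a short script. No extra patients, readers or procedures are needed. The downside is a less familiar measure that also reads lower (about 0.77 against 0.83 for a binary AUC in the 0.7 versus 0.5 example). The unchanged pCR AUC remains for comparison with other studies.

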**STUDY SUMMARY**

Title	Performance of contrast-enhanced spectral mammography to assess neoadjuvant therapy response
Short Title	Contrast-enhanced mammography Assessment of Breast Cancer Neoadjuvant Therapy response
Protocol Number	The standard protocol number used to identify this study
Phase	III
Methodology	Prospective, Single Arm, Unblinded
Study Duration	24 months
Study Center(s)	Single-Center, UTSW Breast Center & Parkland Moody Center for Breast Health
Objectives	
Primary Objectives
 
 
1. To investigate the diagnostic accuracy of Contrast Enhanced Spectral Mammography (CEDM) in predicting early neoadjuvant therapy response and pCR compared to mammography.
 
2. To investigate the correlation accuracy of CEDM pre-operative lesion size and final pathological size, compared to mammography.
 

Number of Subjects	100
Diagnosis and Main Inclusion Criteria	
 
1. 18 years and older male or female patients
 
2. Ipsilateral intact biopsy-proven breast cancer clinical T1-T4 (by imaging)
 
3. Available mammography and ultrasound imaging of the existing index cancer, with orthogonal measurements
 
4. Prior history of ipsilateral or contralateral breast cancer, presenting with a new primary or recurrent disease.
 
5. Patients who were determined to be candidates for either neoadjuvant chemotherapy or neoadjuvant endocrine therapy by the treating physician.
 
6. Women of child-bearing potential and men must agree to use adequate contraception (hormonal or barrier method of birth control; abstinence) prior to study entry, for the duration of study participation, and for days following completion of study participation. Should a woman become pregnant or suspect she is pregnant while participating in this study, she should inform her treating physician immediately.
 

Study Product(s), Dose, Route, Regimen	Contrast-Enhanced Digital Mammography
Duration of administration	N/A
Reference therapy	
Statistical Methodology	Descriptive Statistics will be produced. Spearman rank correlation will be used to measure the agreement between final pathologic and imaging tumor size data. ROC analysis will be used to assess the diagnostic performance of CEDM.

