### 1.3 Other Agents

Contrast Enhanced Digital Mammography (CEDM) is a novel imaging technique, which allows digital mammography to be used with contrast enhancement to depict cancers that would otherwise be occult on standard unenhanced mammography. CEDM is performed with and without i.v. iodine contrast, using the dual energy subtraction technique (20-25). Compared with mammography and US, CEDM improves the sensitivity for breast cancer detection without decreasing specificity (20,21). CEDM digital detector has higher spatial resolution than MRI (i.e. typically pixel sizes 100  $\mu$ m and 1 mm, respectively), revealing

Study Number – Insert PRMC Assigned SCCC- Protocol Number (found on the PRMC approval letter)

---

details that are approximately 10 times better. In contrast to the rapid washout in MRI, enhancement on CEDM in fact persists for at least 10 min after contrast agent infusion. Today CEDM is available commercially for clinical use. It is estimated that over 200,000 CEDM examinations have been performed to date in both research and clinical settings. CEDM costs significantly less compared to MRI. (26). Furthermore, longer time delays between contrast injection and CEDM exposure could result in stronger enhancement and hence better visibility compared to MRI, especially given the much higher spatial resolution of digital mammography. It is unknown whether CEDM can improve the sensitivity of mammography in the early assessment of neoadjuvant therapy response. We hypothesize that CEDM is superior to mammography and ultrasound in assessing early response, and pre-surgical residual cancer after neoadjuvant therapy, and when performed, non-inferior to MRI in assessing the residual disease using the metrics of pCR and RCB.

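### For the categorical pCR call, Section 8.3 item 1 plans no paired estimate, with interval, of the CEDM–mammography difference in sensitivity or specificity

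*Combined protocol and SAP*

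**What the plan says.** The Study Summary gives a comparative primary objective: "To investigate the diagnostic accuracy of Contrast Enhanced Spectral Mammography (CEDM) in predicting early neoadjuvant therapy response and pCR compared to mammography". Section 1.3 states a directional hypothesis: "We hypothesize that CEDM is superior to mammography and ultrasound in assessing early response". Section 2.1.1 gives the same primary objective without a comparator.

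The design is "Prospective, Single Arm, Unblinded". Section 4.0 has patients imaged with mammography at baseline, early and late timepoints, with CEDM within two weeks of each, so the two modalities are read in the same patients.

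Section 8.3 item 1, headed as a comparison of the two tests with histopathology as reference, contains two steps:
- "Sensitivities and specificities in predicting pCR (or RCB0) will be calculated for CEDM and mammography respectively".
- A weighted kappa for "The agreement between CEDM and mammography in categorizing tumor response". Section 6.3 repeats this kappa for the RCB categories.

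Item 2 covers continuous measures. It plans ROC analysis for both modalities, says that the AUCs will be compared, and adds an intraclass correlation. Item 3 plans a Spearman correlation between imaging size and pathologic size.

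Section 8.2 does no formal sample size calculation: "We are proposing to accrue 100 patients for enhanced certainty of our descriptive statistics". It adds "We assume 40% prevalence of pCR" and gives 95% half-widths of at most 0.17 for sensitivities, 0.14 for specificities and 0.12 for AUC. Each is for one modality at a time.

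**The concern.** A reader who wants to know whether CEDM calls pCR more accurately than mammography gets four separate proportions and an agreement coefficient from item 1. The correct interval for a paired difference depends on how many patients are called differently by the two tests, counted separately among pCR and non-pCR patients. Neither the four proportions nor kappa supplies those counts: kappa ignores pathology and pools the two groups.

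Two things are at stake. An informal comparison of two single-modality intervals ignores the pairing and can mislead about the precision of the difference. Section 8.2 also says that the results are meant to help design a larger study comparing modalities, and a paired comparison of that kind is sized from the discordant rates, which the plan does not report.

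**Working it through.** **Inputs.** From Section 8.2: N = 100 and pCR prevalence 40%, so 40 pCR patients (sensitivity) and 60 non-pCR patients (specificity), with 95% intervals. From Section 1.2: mammography sensitivity 54.2% and specificity 86.3% for pCR. Assumed, because the documents give no value: CEDM sensitivity 30/40 = 0.75, mammography 22/40 = 0.55, and the share of discordant patients, which is varied below.

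**1. The plan's own figures.** Half-width at p = 0.5 with continuity correction: 1.96·√(0.25/n) + 1/(2n).
- n = 40: 0.155 + 0.0125 = 0.167 (stated 0.17).
- n = 60: 0.1265 + 0.0083 = 0.135 (stated 0.14).

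Both fit the stated maxima. They confirm that Section 8.2 concerns single proportions and not a difference.

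**2. Kappa cannot rank the tests.** Assumed counts, for a two-category call of complete response or not:

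| | Both CR | CEDM only | Mammography only | Neither |
|---|---|---|---|---|
| pCR (40) | 18 | 12 | 4 | 6 |
| Non-pCR (60) | 3 | 3 | 5 | 49 |

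CEDM sensitivity is 30/40 = 0.75 and specificity 54/60 = 0.90. Mammography has 22/40 = 0.55 and 52/60 = 0.87. The pooled table is 21, 15, 9, 55. Observed agreement is 0.76, chance agreement is (36·30 + 64·70)/10,000 = 0.556, and kappa = (0.76 - 0.556)/(1 - 0.556) = 0.459.

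Swap the modality labels: mammography becomes the better test and kappa stays 0.459. An assumed three-category table gave the same invariance (0.633 with linear weights, 0.697 with quadratic). The plan does not state its weights; the invariance holds for any symmetric set.

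**3. The missing quantity.** Let b be the pCR patients called correctly by CEDM only and c those called correctly by mammography only. The difference is (b - c)/n. The paired score (Tango) interval is the set of δ with |b - c - nδ| / √(n(2q + δ(1 - δ))) ≤ 1.96, where q is the restricted maximum-likelihood estimate of the probability behind c. With n = 40 and the margins fixed at 30/40 and 22/40, the difference is always 0.20:

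| b vs c | Discordance | Tango 95% CI | Exact McNemar p |
|---|---|---|---|
| 8 vs 0 | 20% | 0.09 to 0.35 | 0.008 |
| 10 vs 2 | 30% | 0.03 to 0.37 | 0.039 |
| 11 vs 3 | 35% | 0.02 to 0.38 | 0.057 |
| 12 vs 4 | 40% | 0.004 to 0.38 | 0.077 |
| 13 vs 5 | 45% | -0.01 to 0.39 | 0.096 |
| 14 vs 6 | 50% | -0.02 to 0.40 | 0.115 |

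Treating the two tests as independent samples gives a half-width of 1.96·√(0.55·0.45/40 + 0.75·0.25/40) = 0.204, so -0.004 to 0.404 whatever the discordance. Independence of the two calls within pCR patients would give a discordance of 0.75·0.45 + 0.25·0.55 = 47.5%. Pairing therefore narrows the interval when the two tests tend to agree, and gains little or nothing near that value.

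**4. Planning precision.** Half-width at zero difference: 1.96·√(discordance/n).
- Sensitivity, n = 40: 0.14 at 20%, 0.17 at 30%, 0.22 at 50%.
- Specificity, n = 60: 0.11 at 20%, 0.14 at 30%, 0.18 at 50%.

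**The case against.** The best defence is that the study calls itself exploratory and aims at descriptive statistics, that the objective in Section 2.1.1 has no comparator, and that the primary endpoint is measured as AUC, for which item 2 does plan a comparison. Section 8.3 also allows further exploratory analyses, and the discordant counts could be tabulated from the collected data at any time.

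Much of this stands. A reader might infer that the plan contains no comparison of CEDM with mammography; item 2 shows otherwise. Nor do the documents offer kappa as evidence of accuracy; they present it as agreement, which is what it measures. A point difference can be had by subtraction. It would also be too much to say that separate Spearman coefficients are planned for each modality: item 3 does not say so, and the secondary objective and endpoint in Sections 2.2.1 and 2.4.2 name only CEDM, although the second primary objective in the Summary implies both. The continuity-corrected method in Section 8.2 is a planning method; Section 8.3 names no interval method for sensitivity or specificity.

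Complete pairing is also an inference. Section 4.0 supports it, but the table in Section 5.4 lists CEDM and not mammography, and Section 4.1 equates the low-energy images with standard mammograms. Hence the restriction below to patients with both readings.

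The defence does not close the gap in item 1. The primary endpoint names sensitivity and specificity, item 1 is headed as the comparison, and an interval for a difference is itself a descriptive statistic. Leaving it to analyses chosen as needed makes it a post hoc choice.

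**Conclusion.** The point holds for the categorical pCR call: item 1 plans no paired difference in sensitivity or specificity, no interval for it and no discordant counts, and its kappa cannot show which test is more accurate. Item 2 has a lesser gap, since its AUC comparison names no method for correlated AUCs.

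The size depends on discordance, which the documents do not give. Under the assumed sensitivities the paired score interval excludes zero up to 40% discordance and includes it at 45% and above. The exact McNemar p-value already exceeds 0.05 at 35%. A reader might infer that a paired analysis would establish a difference that the current plan hides; nothing in the documents supports that. Pairing gives the correct interval and no assurance about where it falls. This is a worthwhile improvement to the analysis, and it raises no objection to the sample size.

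**What to change.** - **Section 8.3 item 1:** in patients with both readings, report the paired difference in sensitivity (pCR patients) and in specificity (non-pCR patients), each with a 95% paired score (Tango) interval and the discordant 2x2 counts. McNemar's test is optional. Keep kappa as a description of agreement and state its weights.
- **Section 8.3 item 2:** give the AUC difference with a 95% interval that allows for the pairing, for example DeLong.
- **Section 8.3 item 3:** say whether Spearman coefficients are computed for both modalities. If they are, give their difference with a patient-level bootstrap interval.
- **Section 8.2:** add paired-difference half-widths over a range of assumed discordance, such as 0.14 at 20% and 0.22 at 50% for sensitivity, and 0.11 and 0.18 for specificity.

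The cost is some wording and a few lines of code. No new patients, visits or data are needed.
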